### **Psoriasis Concomitant Medications**

#### **Topical Therapy**

##### **Week 0 to Week 52**

Medicated shampoos containing salicylic acid and bland emollients are allowed on all body regions but should not be used within 24 hours before any study visit. Nonmedicated shampoos may be used on the day of the study visit.

Other topical therapies that could affect psoriasis evaluations including but not limited to topical corticosteroids, topical calcineurin inhibitors, vitamin D analogs, vitamin A analogs, retinoids, tar, anthralin, calcipotriene, tazarotene, methoxsalen, trimethylpsoralens, fumarate, PDE4 inhibitors, topical JAK inhibitors, aryl hydrocarbon receptor-modulating agents; shampoos that contain corticosteroids, coal tar, or vitamin D3 analogs; and herbal treatments and traditional Taiwanese, Korean, or Chinese medicines are not permitted.

##### **Week 52 to Week 160**

After the Week 52 visit, most topical therapies are permitted for treatment of psoriasis; ultra-high potency corticosteroids and topical JAK inhibitors are still prohibited during this period.

#### **Phototherapy or Systemic Therapy**

The use of phototherapy or systemic medications that could affect psoriasis evaluations is not permitted at any time during the study.

These medications include:

- those targeted for reducing TNF $\alpha$  (including but not limited to adalimumab, infliximab, or etanercept).

- drugs targeted for reducing IL-12/23, IL17, or IL-23 (including but not limited to ustekinumab, briakinumab, guselkumab, tildrakizumab, secukinumab, risankizumab, ixekizumab, or brodalumab).
- alpha-4 integrin antagonists (including but not limited to natalizumab).
- JAK inhibitors (including but not limited to TYK2 inhibitors).
- PDE4 inhibitors (including but not limited to apremilast).
- oral and injectable (IV, intramuscular, or intralesional) corticosteroids.
- any other conventional systemic therapies that could affect psoriasis evaluations (including but not limited to methotrexate, cyclosporine A, acitretin, or other retinoids).
- antimalarial agents.
- herbal treatments.
- traditional Taiwanese, Korean, or Chinese medicines.

### **Concomitant Medications for Indications Other Than Psoriasis**

The use of systemic corticosteroids for indications other than psoriasis should be limited to situations for which, in the opinion of the treating physician, there are no adequate alternatives. Systemic corticosteroids should be used on a short-term basis, preferably for  $\leq 2$  weeks. Longer term use of corticosteroids should be discussed with the medical monitor or designee and may require discontinuation of study intervention. Inhaled, otic, ocular, nasal, or other routes of mucosal delivery of corticosteroids are allowed throughout the study. After Week 52, intra-articular corticosteroids are allowed for indications other than psoriasis. Vitamin D3 and analogs for dietary supplementation are permitted.

## **6.8. Appendix 8 Laboratory Toxicity Grading**

The grading scale use for lab assessments is based on ‘CCTCAE’.

If a laboratory value falls within the grading as specified below but also within the laboratory normal limits, the value is considered to be normal and will be reset to grade 0.

Pre-baseline measurements will use the same grading ranges as applied to baseline measurements. In case a test has two sets of ranges – one for baseline normal and one for baseline abnormal, the one for baseline normal will be applied for all measurements taken pre-baseline and on baseline.

Text in gray italic in the table is present in the grading scale, but is not applied by J&J when grading lab data.

CTCAE Term	Grade 1	Grade 2	Grade 3	Grade 4	J&J Implementation Notes
Blood and lymphatic system disorders					
Anemia	Hemoglobin (Hgb) <LLN - 10.0 g/dL; <LLN - 6.2 mmol/L; <LLN - 100 g/L	Hemoglobin (Hgb) <10.0 - 8.0 g/dL; <6.2 - 4.9 mmol/L; <100 - 80g/L	Hemoglobin (Hgb) <8.0 g/dL; <4.9 mmol/L; <80 g/L; transfusion indicated	Life-threatening consequences; urgent intervention indicated	Clinical signs and symptoms are not taken into consideration for grading.
Leukocytosis	-	-	>100,000/mm  ; >100 x 10  /L	Clinical manifestations of leucostasis; urgent intervention indicated	Clinical signs and symptoms are not taken into consideration for grading; Added ranges in SI unit (x 10  /L)
Investigations					
Activated partial thromboplastin time prolonged	>ULN - 1.5 x ULN	>1.5 - 2.5 x ULN	>2.5 x ULN; bleeding	-	Clinical signs and symptoms are not taken into consideration for grading.
Alanine aminotransferase increased	>ULN - 3.0 x ULN if baseline was normal; 1.5 - 3.0 x baseline if baseline was abnormal	>3.0 - 5.0 x ULN if baseline was normal; >3.0 - 5.0 x baseline if baseline was abnormal	>5.0 - 20.0 x ULN if baseline was normal; >5.0 - 20.0 x baseline if baseline was abnormal	>20.0 x ULN if baseline was normal; >20.0 x baseline if baseline was abnormal	Ranges defined for “abnormal baseline” are applied only if baseline > ULN. If baseline < LLN, then ranges for “normal baseline” are applied.
Alkaline phosphatase increased	>ULN - 2.5 x ULN if baseline was normal; 2.0 - 2.5 x baseline if baseline was abnormal	>2.5 - 5.0 x ULN if baseline was normal; >2.5 - 5.0 x baseline if baseline was abnormal	>5.0 - 20.0 x ULN if baseline was normal; >5.0 - 20.0 x baseline if baseline was abnormal	>20.0 x ULN if baseline was normal; >20.0 x baseline if baseline was abnormal	Ranges defined for “abnormal baseline” are applied only if baseline > ULN. If baseline < LLN, then ranges for “normal baseline” are applied.
Aspartate aminotransferase increased	>ULN - 3.0 x ULN if baseline was normal; 1.5 - 3.0 x baseline if baseline was abnormal	>3.0 - 5.0 x ULN if baseline was normal; >3.0 - 5.0 x baseline if baseline was abnormal	>5.0 - 20.0 x ULN if baseline was normal; >5.0 - 20.0 x baseline if baseline was abnormal	>20.0 x ULN if baseline was normal; >20.0 x baseline if baseline was abnormal	Ranges defined for “abnormal baseline” are applied only if baseline > ULN. If baseline < LLN, then ranges for “normal baseline” are applied.
Blood bilirubin increased	>ULN - 1.5 x ULN if baseline was normal;	>1.5 - 3.0 x ULN if baseline was normal;	>3.0 - 10.0 x ULN if baseline was normal;	>10.0 x ULN if baseline was normal;	Ranges defined for “abnormal baseline” are

CTCAE Term	Grade 1	Grade 2	Grade 3	Grade 4	J&J Implementation Notes
	> 1.0 - 1.5 x baseline if baseline was abnormal	>1.5 - 3.0 x baseline if baseline was abnormal	>3.0 - 10.0 x baseline if baseline was abnormal	>10.0 x baseline if baseline was abnormal	applied only if baseline > ULN. If baseline < LLN, then ranges for “normal baseline” are applied.
CD4 lymphocytes decreased	<LLN - 500/mm  ; <LLN - 0.5 x 10  /L	<500 - 200/mm  ; <0.5 - 0.2 x 10  /L	<200 - 50/mm  ; <0.2 x 0.05 - 10e9 /L	<50/mm  ; <0.05 x 10e9 /L	
Cholesterol high	>ULN - 300 mg/dL; >ULN - 7.75 mmol/L	>300 - 400 mg/dL; >7.75 - 10.34 mmol/L	>400 - 500 mg/dL; >10.34 - 12.92 mmol/L	>500 mg/dL; >12.92 mmol/L	
CPK increased	>ULN - 2.5 x ULN	>2.5 x ULN - 5 x ULN	>5 x ULN - 10 x ULN	>10 x ULN	CPK (Creatine Phosphokinase) and CK (Creatine Kinase) are synonyms
Creatinine increased	>ULN - 1.5 x ULN	>1.5 - 3.0 x baseline; >1.5 - 3.0 x ULN	>3.0 x baseline; >3.0 - 6.0 x ULN	>6.0 x ULN	
Fibrinogen decreased	<1.0 - 0.75 x LLN; if abnormal, <25% decrease from baseline	<0.75 - 0.5 x LLN; if abnormal, 25 - <50% decrease from baseline	<0.5 - 0.25 x LLN; if abnormal, 50 - <75% decrease from baseline	<0.25 x LLN; if abnormal, 75% decrease from baseline; absolute value <50 mg/dL	Ranges defined for “abnormal” are applied only on values < LLN. Grade 0 will be assigned to values > ULN.
GGT increased	>ULN - 2.5 x ULN if baseline was normal; 2.0 - 2.5 x baseline if baseline was abnormal	>2.5 - 5.0 x ULN if baseline was normal; >2.5 - 5.0 x baseline if baseline was abnormal	>5.0 - 20.0 x ULN if baseline was normal; >5.0 - 20.0 x baseline if baseline was abnormal	>20.0 x ULN if baseline was normal; >20.0 x baseline if baseline was abnormal	Ranges defined for “abnormal baseline” are applied only if baseline > ULN. If baseline < LLN, then ranges for “normal baseline” are applied.
Haptoglobin decreased	<LLN	-	-	-	
Hemoglobin increased	Increase in >0 - 2 g/dL; Increase in >0 - 20 g/L	Increase in >2 - 4 g/dL; Increase in >20 - 40 g/L	Increase in >4 g/dL; Increase in >40 g/L	-	The increase indicates the level of increase above normal (above ULN). Applied as, e.g. grade 1 (g/dL): >ULN – ULN+2 g/dL; Added ranges in SI unit (g/L).
INR increased	>1.2 - 1.5; >1 - 1.5 x baseline if on anticoagulation;	>1.5 - 2.5; >1.5 - 2.5 x baseline if on anticoagulation;	>2.5; >2.5 x baseline if on anticoagulation; bleeding	-	Concomitant therapy or clinical signs and symptoms are not taken

CTCAE Term	Grade 1	Grade 2	Grade 3	Grade 4	J&J Implementation Notes
	monitoring only indicated	dose adjustment indicated			into consideration for grading.
Lipase increased	>ULN - 1.5 x ULN	>1.5 - 2.0 x ULN; >2.0 - 5.0 x ULN and asymptomatic	>2.0 - 5.0 x ULN with signs or symptoms; >5.0 x ULN and asymptomatic	>5.0 x ULN and with signs or symptoms	“Asymptomatic” ranges are not taken into consideration for grading, i.e. worst case grading is applied.
Lymphocyte count decreased	<LLN - 800/mm  ; <LLN - 0.8 x 10  /L	<800 - 500/mm  ; <0.8 - 0.5 x 10  /L	<500 - 200/mm  ; <0.5 - 0.2 x 10  /L	<200/mm  ; <0.2 x 10  /L	
Lymphocyte count increased	-	>4000/mm  - 20,000/mm  ; >4 - 20 x 10  /L	>20,000/mm  ; >20 x 10  /L	-	Added ranges in SI unit (x 10  /L).
Neutrophil count decreased	<LLN - 1500/mm  ; <LLN - 1.5 x 10  /L	<1500 - 1000/mm  ; <1.5 - 1.0 x 10  /L	<1000 - 500/mm  ; <1.0 - 0.5 x 10  /L	<500/mm  ; <0.5 x 10  /L	Both Neutrophils and segmented neutrophils are graded using these criteria.
Platelet count decreased	<LLN - 75,000/mm  ; <LLN - 75.0 x 10  /L	<75,000 - 50,000/mm  ; <75.0 - 50.0 x 10  /L	<50,000 - 25,000/mm  ; <50.0 - 25.0 x 10  /L	<25,000/mm  ; <25.0 x 10  /L	
Serum amylase increased	>ULN - 1.5 x ULN	>1.5 - 2.0 x ULN; >2.0 - 5.0 x ULN and asymptomatic	>2.0 - 5.0 x ULN with signs or symptoms; >5.0 x ULN and asymptomatic	>5.0 x ULN and with signs or symptoms	“Asymptomatic” ranges are not taken into consideration for grading, i.e. worst case grading is applied.
White blood cell decreased	<LLN - 3000/mm  ; <LLN - 3.0 x 10  /L	<3000 - 2000/mm  ; <3.0 - 2.0 x 10  /L	<2000 - 1000/mm  ; <2.0 - 1.0 x 10  /L	<1000/mm  ; <1.0 x 10  /L	
Metabolism and nutrition disorders					
Acidosis	pH <normal, but ≥7.3	-	pH <7.3	Life-threatening consequences	pH <normal is implemented as pH <LLN. Clinical signs and symptoms are not taken into consideration for grading.
Alkalosis	pH >normal, but ≤7.5	-	pH >7.5	Life-threatening consequences	pH >normal is implemented as pH >ULN. Clinical signs and symptoms are not taken

CTCAE Term	Grade 1	Grade 2	Grade 3	Grade 4	J&J Implementation Notes
					into consideration for grading.
Hypercalcemia	Corrected serum calcium of >ULN - 11.5 mg/dL; >ULN - 2.9 mmol/L;  Ionized calcium >ULN - 1.5 mmol/L	Corrected serum calcium of >11.5 - 12.5 mg/dL; >2.9 - 3.1 mmol/L;  Ionized calcium >1.5 - 1.6 mmol/L;  symptomatic	Corrected serum calcium of >12.5 - 13.5 mg/dL; >3.1 - 3.4 mmol/L;  Ionized calcium >1.6 - 1.8 mmol/L;  hospitalization indicated	Corrected serum calcium of >13.5 mg/dL; >3.4 mmol/L;  Ionized calcium >1.8 mmol/L;  life-threatening consequences	Clinical signs and symptoms are not taken into consideration for grading. Note: For Hypercalcemia or Hypocalcemia in the CTCAE Lab Toxicity grading scale, the reference ranges from serum calcium (ULN /LLN) from the local or central lab are being utilized.
Hyperkalemia	Potassium >ULN - 5.5 mmol/L	Potassium >5.5 - 6.0 mmol/L; intervention initiated	Potassium >6.0 - 7.0 mmol/L; hospitalization indicated	Potassium >7.0 mmol/L; life-threatening consequences	Clinical signs and symptoms are not taken into consideration for grading.
Hypermagnesemia	Magnesium >ULN - 3.0 mg/dL; >ULN - 1.23 mmol/L	-	Magnesium >3.0 - 8.0 mg/dL; >1.23 - 3.30 mmol/L	Magnesium >8.0 mg/dL; >3.30 mmol/L; life-threatening consequences	Clinical signs and symptoms are not taken into consideration for grading.
Hypernatremia	Sodium >ULN - 150 mmol/L	Sodium >150 - 155 mmol/L; intervention initiated	Sodium >155 - 160 mmol/L; hospitalization indicated	Sodium >160 mmol/L; life-threatening consequences	Clinical signs and symptoms are not taken into consideration for grading.
Hypertriglyceridemia	Triglycerides 150 mg/dL - 300 mg/dL; 1.71 mmol/L - 3.42 mmol/L	Triglycerides >300 mg/dL - 500 mg/dL; >3.42 mmol/L - 5.7 mmol/L	Triglycerides >500 mg/dL - 1000 mg/dL; >5.7 mmol/L - 11.4 mmol/L	Triglycerides >1000 mg/dL; >11.4 mmol/L; life-threatening consequences	Clinical signs and symptoms are not taken into consideration for grading.
Hypoalbuminemia	Albumin <LLN - 3 g/dL; <LLN - 30 g/L	Albumin <3 - 2 g/dL; <30 - 20 g/L	Albumin <2 g/dL; <20 g/L	Life-threatening consequences; urgent intervention indicated	Clinical signs and symptoms are not taken into consideration for grading.

CTCAE Term	Grade 1	Grade 2	Grade 3	Grade 4	J&J Implementation Notes
Hypocalcemia	Corrected serum calcium of <LLN - 8.0 mg/dL; <LLN - 2.0 mmol/L;  Ionized calcium <LLN - 1.0 mmol/L	Corrected serum calcium of <8.0 - 7.0 mg/dL; <2.0 - 1.75 mmol/L;  Ionized calcium <1.0 - 0.9 mmol/L;  symptomatic	Corrected serum calcium of <7.0 - 6.0 mg/dL; <1.75 - 1.5 mmol/L;  Ionized calcium <0.9 - 0.8 mmol/L;  hospitalization indicated	Corrected serum calcium of <6.0 mg/dL; <1.5 mmol/L;  Ionized calcium <0.8 mmol/L;  life-threatening consequences	Clinical signs and symptoms are not taken into consideration for grading. Note: For Hypercalcemia or Hypocalcemia in the CTCAE Lab Toxicity grading scale, the reference ranges from serum calcium (ULN /LLN) from the local or central lab are being utilized.
Hypoglycemia	Glucose <LLN - 55 mg/dL; <LLN - 3.0 mmol/L	Glucose <55 - 40 mg/dL; <3.0 - 2.2 mmol/L	Glucose <40 - 30 mg/dL; <2.2 - 1.7 mmol/L	Glucose <30 mg/dL; <1.7 mmol/L; life-threatening consequences; seizures	Clinical signs and symptoms are not taken into consideration for grading. Urine glucose is not graded.
Hypokalemia	Potassium <LLN - 3.0 mmol/L	Symptomatic with Potassium <LLN - 3.0 mmol/L; intervention indicated	Potassium <3.0 - 2.5 mmol/L; hospitalization indicated	Potassium <2.5 mmol/L; life-threatening consequences	“Symptomatic” ranges are applied for grade 2, grade 1 not assigned, i.e. worst case applied. Clinical signs and symptoms are not taken into consideration for grading of grade 3 and 4.
Hypomagnesemia	Magnesium <LLN - 1.2 mg/dL; <LLN - 0.5 mmol/L	Magnesium <1.2 - 0.9 mg/dL; <0.5 - 0.4 mmol/L	Magnesium <0.9 - 0.7 mg/dL; <0.4 - 0.3 mmol/L	Magnesium <0.7 mg/dL; <0.3 mmol/L; life-threatening consequences	Clinical signs and symptoms are not taken into consideration for grading.
Hyponatremia	Sodium <LLN - 130 mmol/L	Sodium 125-129 mmol/L and asymptomatic	Sodium 125-129 mmol/L symptomatic; 120-124 mmol/L regardless of symptoms	Sodium <120 mmol/L; life-threatening consequences	Clinical signs and symptoms are not taken into consideration for grading.

CTCAE Term	Grade 1	Grade 2	Grade 3	Grade 4	J&J Implementation Notes
			Sodium <130-120 mmol/L		Worst case (“<130-120 mmol/L” for grade 3 added by J&J) is applied across grade 2/3 ranges: 120-129 mol/L assigned to grade 3, grade 2 not used.
Renal and urinary disorders					
Proteinuria	1+ proteinuria; urinary protein $\geq$ ULN - <1.0 g/24 hrs; urinary protein $\geq$ ULN - <1000 mg/day	Adult: 2+ and 3+ proteinuria; urinary protein 1.0 - <3.5 g/24 hrs; urinary protein 1000 - <3500 mg/day  Pediatric: Urine P/C (Protein/Creatinine) ratio 0.5 - 1.9; Urine P/C (Protein/Creatinine) 56.5 – 214.7 g/mol	Adult: 4+ proteinuria; urinary protein $\geq$ 3.5 g/24 hrs; urinary protein $\geq$ 3500 mg/day;  Pediatric: Urine P/C (Protein/Creatinine) ratio >1.9; Urine P/C (Protein/Creatinine) >214.7 g/mol	-	In case both 24-h urine collection and dipstick are collected, then worst case is taken, as opposed to having 24-h urine collection take precedence over dipstick. Added ranges in SI unit for urinary protein (mg/day) and for urine P/C (g/mol). Pediatric grading is applied to age range [0-18]. Adult grading is applied for ages [ $>18$ ].

\* Grade 0 is assigned to a lab assessment when the lab test is described in the table, but the lab value is not assigned a grade 1 or higher.

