9.3.1. General Considerations

Simple descriptive summary statistics, such as n, mean, SD, median, interquartile range, minimum, and maximum for continuous variables, and counts and percentages for discrete variables will be used to summarize most data.

For binary endpoints, treatment comparisons will be performed using a CMH test stratified by age group at screening (adolescents <18 years and adults ≥18 years), baseline weight category for adults (≤90kg, >90kg) and geographic region. In case of rare events for binary endpoints, Fisher's exact test will be used. For repeated measure continuous endpoints, treatment comparisons will be performed using a MMRM model. The MMRM will include treatment, age group (adolescents <18 years and adults ≥18 years), baseline weight, geographic region and baseline value, as explanatory factors. The MMRM model will also include visit, treatment group by visit interaction, and baseline value by visit interaction as additional explanatory factors. The LS mean estimates and their corresponding 95% CI will be provided at each timepoint. In addition, the estimates of LS mean difference and 95% CIs between treatment groups will be provided. Analysis of

covariance will be used to analyze some continuous endpoints when appropriate. The ANCOVA will include treatment group, baseline value, weight, geographic region and age group. The LS mean estimates and their corresponding 95% CI will be provided. In addition, LS mean difference and 95% CIs between treatment groups will be provided. For time to event endpoints, treatment comparisons will be performed using a log-rank test stratified by baseline weight category for adults (≤ 90 kg, >90 kg), geographic region and age group. Kaplan-Meier or life-table estimates of cumulative rate by treatment group will be provided to evaluate the timing of event occurrence in different treatment groups.

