10. SUPPORTING DOCUMENTATION AND OPERATIONAL CONSIDERATIONS

10.1. Appendix 1: Clinical Laboratory Tests

The following tests will be performed according to the Schedule of Activities (SoA).

The actual date of assessment and, if required, the actual time of the assessment of laboratory samples will be recorded in the source documentation and in the eCRF or laboratory requisition form.

Protocol-Required Laboratory Assessments

Laboratory Assessments	Parameters		
Hematology	Platelet count Red blood cell count Hemoglobin Hematocrit	RBC Indices: Mean corpuscular volume (MCV) Mean corpuscular hemoglobin (MCH) % Reticulocytes	White Blood Cell (WBC) count with Differential: Neutrophils Lymphocytes Monocytes Eosinophils Basophils
	Note: A WBC evaluation may include any abnormal cells, which will then be reported by the laboratory. An RBC evaluation may include abnormalities in the RBC count, RBC parameters, or RBC morphology, which will then be reported by the laboratory. In addition, any other abnormal cells in a blood smear will also be reported.		
Clinical Chemistry	Sodium Potassium Chloride Bicarbonate Blood urea nitrogen (BUN) Creatinine Glucose (nonfasting) Aspartate aminotransferase (AST)/Serum glutamic-oxaloacetic Alanine aminotransferase (ALT)/Serum glutamic-oxaloacetic Gamma-glutamyltransferase (GGT) estimated glomerular filtration rate (eGFR)*	Total and direct bilirubin (Tbili and Dbil) Alkaline phosphatase Creatine phosphokinase (CPK) Lactic acid dehydrogenase (LDH) Uric acid Calcium Phosphate Albumin Total protein Cholesterol Triglycerides Magnesium	
Lipid Panel	Total cholesterol High-density lipoprotein (HDL) Low-density lipoprotein (LDL; calculated) Triglycerides Note: Fasting requirements are described in the SoA (Section 1.3).		

Laboratory Assessments	Parameters	
Routine Urinalysis	Dipstick Specific gravity pH Glucose Protein Blood Ketones Bilirubin Urobilinogen Nitrite Leukocyte esterase	Sediment (if dipstick result is abnormal) Red blood cells White blood cells Epithelial cells Crystals Casts Bacteria
	If dipstick result is abnormal, microscopy will be used to measure sediment. In the microscopic examination, observations other than the presence of WBC, RBC and casts may also be reported by the laboratory.	

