### 4.5.3. Additional Safety Assessments

#### 4.5.3.1. Clinical Laboratory Tests

Clinical laboratory tests will be displayed for the participants included in the safety analysis set.

Box plots of laboratory measurements and change from baseline will be provided for the select laboratory measurements. In addition, box plot for select laboratory measurements may be provided among adolescent participants.

Applicable laboratory results will be graded according to National Cancer Institute's Common Terminology Criteria for Adverse Events (NCI-CTCAE). The proportion of participants with post-baseline values by maximum toxicity grade for clinical laboratory tests will be summarized overall and by age group. Participants with toxicity grades  $\geq 2$  will be listed.

In addition, for selected laboratory parameters (i.e. ALT, AST), ULN will also be used to identify abnormal laboratory test results. Lipid and hs-CRP will be summarized. The 4-week window after the last dose or treatment discontinuation will be applied.

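### SAP Appendix 8 grades dipstick protein of 2+ to 4+ for adults only; read with its Grade 0 footnote, an adolescent's 4+ ranks below a 1+, and 18-year-old adults fall under the same rule

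*SAP*

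**What the plan says.** The proteinuria row of SAP Appendix 8 (section 6.8) has three graded columns.

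- **Grade 1** has no age label: "1+ proteinuria; urinary protein" from the upper limit of normal to below 1.0 g per 24 hours.
- **Grade 2** is split by age. The adult cell includes "2+ and 3+ proteinuria". The paediatric cell is a urine protein/creatinine ratio of 0.5 to 1.9 and has no dipstick criterion.
- **Grade 3** is split in the same way: 4+ (or 24-hour protein) for adults, a ratio above 1.9 for paediatric participants.

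The implementation note sets the age bands: "Pediatric grading is applied to age range [0-18"] and "Adult grading is applied for ages" above 18. The table footnote covers results that meet no cell at Grade 1 or above, in words that begin: "Grade 0 is assigned to a lab assessment when the lab test is described in the table, but the lab value is not assigned a".

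Protocol Appendix 1 (section 10.1) lists routine urinalysis as a dipstick that includes protein, with one reflex test: "If dipstick result is abnormal, microscopy will be used to measure sediment". It lists no urine creatinine, ratio or 24-hour collection, and the Schedules of Activities add none.

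Protocol section 9.3.1 defines "age group at screening (adolescents <18 years", with adults being 18 or over. SAP section 4.1 does the same. SAP section 4.5.3.1 says that maximum toxicity grades for "clinical laboratory tests will be summarized overall and by age group", and that participants with Grade 2 or above are listed.

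**The concern.** A severity scale should not give a worse result a lower grade. For adolescents this row appears to do so, because the only route to Grades 2 and 3 needs a measurement the protocol does not ask for. The age bands then extend the rule to 18-year-olds, whom the trial stratifies, randomizes and analyses as adults.

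What is at stake is how the safety tables are read. If proteinuria is graded, the age-group summary will show no adolescent at Grade 2 or above, and the listing will contain none. A reader could take that as a finding when the rule makes it inevitable. Dipstick protein is collected often: 12 visits from Week 0 to Week 52 and five more from Week 64 to Week 156. Protocol section 2.3.3 says that direct benefits and risks in adolescents have not been established in earlier trials, although it expects them to match those in adults.

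**Working it through.** The plan states no figure to reproduce. The check applies the rule as written.

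**Inputs.** From SAP Appendix 8: the row's cut-offs and age labels, the bands 0 to 18 and above 18, and the Grade 0 footnote. From Protocol Appendix 1 and the Schedules of Activities: dipstick protein available, ratio not available. From Protocol section 4.1: about 60 adolescents among 600 participants, randomized 2:1.

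**Rule.** Grade = the highest cell met; Grade 0 if no cell is met.

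| Age | Trial group | 1+ | 2+ | 3+ | 4+ |
|---|---|---|---|---|---|
| 12 | adolescent | 1 | 0 | 0 | 0 |
| 17 | adolescent | 1 | 0 | 0 | 0 |
| 18 | adult | 1 | 0 | 0 | 0 |
| 19 | adult | 1 | 2 | 2 | 3 |
| 40 | adult | 1 | 2 | 2 | 3 |

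Up to and including age 18 the order is inverted: 1+ outranks 4+, and Grades 2 and 3 cannot be reached.

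**Is the row simply garbled?** The two unit conversions for the ratio agree (56.5 / 0.5 = 113.0 and 214.7 / 1.9 = 113.0), so the paediatric cells read as intended.

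**Does the result depend on the footnote?** Only in part. If adolescent results above 1+ were capped at Grade 1, or left ungraded, the inversion would disappear, but Grade 2 would still be out of reach and the listing would still omit them.

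**Who is affected.** 60 / 600 = 10% of participants. At 2:1, 60 x 2/3 = 40 start on JNJ-77242113 and 20 on placebo. The number of 18-year-olds is not given. It also depends on whether age is in completed years and at what date it is taken, neither of which Appendix 8 states.

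**How many results.** The documents give no rate of 2+ or more in adolescents. Assuming that 1% to 5% have at least one such result, 60 x 0.01 = 0.6 and 60 x 0.05 = 3, that is, 0.6 to 3 participants.

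**The case against.** The strongest reply is that proteinuria may not be graded in this trial at all. SAP section 4.5.3.1 grades only applicable results. Protocol section 9.3.5 names hematology and chemistry for the summary of abnormal laboratory values. Appendix 8 is evidently a generic sponsor table, since it also grades tests the protocol does not list, such as CD4 count and haptoglobin. This limits the certainty of the effect but does not remove the point. The Grade 2-or-higher listing in Protocol section 9.3.5 carries no such restriction, and dipstick protein is collected. Where the sponsor does not grade a urine test it says so, as the hypoglycemia row does for urine glucose. The proteinuria note instead explains how to combine dipstick and 24-hour results.

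Second, no sentence says that a paediatric 2+ is Grade 0. That is right: it follows from the age labels and the footnote together. The table takes the worst case elsewhere, so the inversion is unlikely to be intended. An unintended result still needs correcting.

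Three stronger readings are tempting, and the documents do not support them:

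- *The ratio is never collected.* Protocol Appendix 1 defers further detail to the laboratory manual, which is not among the documents, and Protocol section 8.4.3 requires supplemental tests when medically indicated. All that can be said is that the ratio is not a protocol-required test.
- *The adolescent renal picture will be falsely clean.* Serum creatinine is collected and graded with no age split. Investigators must review laboratory results and record clinically relevant changes as adverse events (Protocol section 8.3.3), and overall adverse events are summarized by age group (SAP section 4.5.2).
- *Adult dipstick grades are the only acceptable remedy.* They depart from the scale's paediatric cell, so explicit non-grading with a listing is equally defensible.

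**Conclusion.** The point holds within those limits. As written, Appendix 8 gives no workable grade for adolescent dipstick protein above 1+, and its default ranks those results below 1+. On protocol-required data no adolescent can appear in the Grade 2-or-higher listing for proteinuria. The age band contradicts the trial's own definition and puts 18-year-old adults under the same rule.

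The size is small: one row of descriptive safety output, about 60 adolescents exposed to the rule, and probably a few participants at most with a result that would be misreported. That last figure rests on the assumed 1% to 5%. The conclusion also assumes that proteinuria counts as an applicable result and that no ratio is obtained outside the protocol-required tests. No efficacy endpoint, alpha or power is affected, and no formal safety comparison is planned. The harm is to reporting, not to detection of a case at the site. The correction is nonetheless worth making, because the rule yields a wrong order and the data needed to avoid it are already collected.

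**What to change.** Amend the proteinuria row and notes in SAP Appendix 8.

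1. Replace the age bands with <18 and >=18, using age at screening, to match the stratification. This also stops a participant's grading rule from changing with a birthday during the study.
2. State what happens when no protein/creatinine ratio is available for an adolescent, choosing one of two options:
   - apply the dipstick cut-offs already in the table (2+/3+ to Grade 2, 4+ to Grade 3), with a footnote that this departs from the paediatric cell; or
   - state that adolescent dipstick protein is not CTCAE-graded, exempt it from the Grade 0 default, and list all adolescents with 2+ or more alongside the Grade 2-or-higher listing.

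The cost is a short SAP note and a minor programming change, with no new data collection. The first option gives one scale across ages at the price of the footnoted departure. The second keeps the paediatric cell intact but adds a listing.
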